8.2. Main trial outcomes

8.2.1. Primary outcome(s)

Health related quality of life at 6 months post-randomisation, as measured by the total score on the K-BILD questionnaire

8.2.2. Secondary outcomes

All secondary outcomes are measured at 6 months post-randomisation unless otherwise stated.

8.2.2.1 Clinical

- Subscales within K-BILD (breathlessness, activity, chest symptoms)
- MRC Score
- Exercise capacity using the 6MWT or 1 minute sit to stand
- Physical activity using the IPAQ
- Sleepiness using the Epworth Sleepiness Scale
- Hospitalisations (all cause and IPF specific)
- Cough using a 6 point VAS
- Targeted adverse events
- Mortality (6 months, and from medical record only at 12 months)

- Medication use: benzodiazepines, antifibratics; ACEis and opiates for breathlessness.
- Completion of pulmonary rehabilitation
- Scheduled and unscheduled health service use relating to IPF.

8.2.2.2 Economic

To assess the cost effectiveness of AOT compared to the standardised breathlessness advice alone at 6 months after using the trial allocation using EQ-5D-5L and scheduled and unscheduled health service use relating to IPF.

8.2.2.3 Mechanistic

Haemoglobin and haematocrit, which are measures of secondary effects of chronic hypoxia – rises in either would indicate a lack of effectiveness of AOT, or disease progression by way of development of chronic respiratory failure. They are a required safety measure as well, as development of secondary rises in either measure would be an indication for routine oxygen treatment.

Physical activity data will also be obtained via an accelerometer in a subset of 20% of trial participants (n=52; 26 participants from each trial arm), and associated processing software for how many minutes per day somebody is active in terms of intensity of exercise: sedentary; low; moderate; high. Accelerometers will be worn by the participant for 7 days after randomisation prior to commencing the trial allocation. It will then also be worn for 7 days prior to their final trial visit.

8.2.2.4 Qualitative

These are outlined in the internal pilot outcomes in section 8.1.2.

9. TRIAL PROCEDURES

The following should be performed/collected at baseline:

Clinic visit 1 (Baseline):

- Weight & Height
- Medical history
- Smoking status
- Shortness of breath (MRC dyspnoea score)
- Spirometry within the last 6 months
- Blood Gases (if saturations are <90% on air as per usual care)
- Full Blood Count (FBC/CBC) and storage of plasma for translational work
- Gas Transfer Test within the last 6 months
- Lung function tests
- Assessment of desaturation both on and off oxygen via either the 6MWT or 1 minute sit to stand
- Completion of the participant completed booklet

In addition, at the baseline visit, following randomisation, advice on breathlessness should be given to all participants, and for those randomised to the AOT arm, the oxygen prescription should be provided. For those centres taking part in the sub-study, interest by the participant in taking part in the sub-study should be ascertained.

The following should take place at the 3 week telephone follow up:

3 weeks post randomisation for AOT arm only:

- Telephone (3 weeks post randomisation) **Completed by staff at BCTU.**

- *The timescale as to when this telephone call takes place depends on when the participant receives the AOT. Depending on site/demand, this may take 2-3 weeks following referral to the oxygen team following randomisation.*

The following should be performed at 3 months follow up:

Clinic Visit 2 (3 months) *May be conducted via video depending on local policy*

- Review prescription for Study
- Survival Check
- SAE
- Completion of EQ-5D-L
- Healthcare utilisation
- SpO₂ check

The following should be performed/collected at 6 months follow up:

Clinic Visit 3 (6 months)

- Survival Check
- SAE Check
- Clinical review
- Check completion of HRQoL
- Blood Gases (if saturations are <90% on air as per usual care)
- Full Blood Count (FBC/CBC) and storage of plasma for translational work
- Recording of lung function (spirometry and gas transfer) if done as part of usual care
- Check completion of HRQoL
- Healthcare utilisation
- Weight
- Smoking status
- Shortness of breath (MRC dyspnoea score)
- Assessment of desaturation both on and off oxygen via either 6MWT or 1 minute sit to stand

9.1. Schedule of assessments

Table 2: Schedule of Assessments

Event	Pre-screening	Visit 1: Baseline	Telephone call: 3 week (done by BCTU)	Visit 2: 3 months	Visit 3: 6 months
Inclusion	X	X			
Exclusion	X	X			
Consent		X			
FVC & DLCO		X			X
6MWT on/off oxygen		X			X
Randomisation		X			
Standardised breathlessness advice		X			
Demographics		X			
Medical history		X			
Pulmonary rehabilitation date and/or completion date		X			X
Medications (including LTOT)		X			X
KBILD		X			X
MRC, cough by VAS		X			X
IPAQ		X			X
Accelerometer*		X			X
Trial fidelity			X		
Adverse events		X		X	X
EQ-5D-5L		X		X	X
Healthcare utilisation		X		X	X
Observations including oxygen sats		X		X	X
Clinical review		X		X	X

10. Withdrawal and changes in levels of participation

Informed consent is defined as the process of learning the key facts about a clinical trial before deciding whether or not to participate. It is a continuous and dynamic process and participants should be asked about their ongoing willingness to continue participation.

Participants should be aware from the beginning that they can freely withdraw (cease to participate) from the trial at any time. A participant may wish to cease to participate in a *particular* aspect of the trial.

The changes in levels of participation within the trial are categorised in the following ways:

- **No trial intervention:** The participant would no longer like to receive the trial treatment, but is willing to be followed up in accordance with the schedule of assessments and if applicable using any central UK NHS bodies for long-term outcomes (i.e. the participant has agreed that data can be collected and used in the trial analysis)
- **No trial related follow-up:** The participant would like to withdraw from trial treatment and does not wish to attend trial visits in accordance with the schedule of assessments but is willing to be followed up at standard clinic visits and if applicable using any central UK NHS bodies for long-term outcomes (i.e. the participant has agreed that data can be collected at standard clinic visits and used in the trial analysis, including data collected as part of long-term outcomes)
- **No further data collection:** The participant is not willing to be followed up in any way for the purposes of the trial and does not wish for any further data to be collected (i.e. only data collected prior to any changes of level in participation can be used in the trial analysis)
- **Sub-study withdrawal:** The participant wishes to withdraw specifically, and only, from the sub-study (Qualitative or actigraph study).

The details of changes of level in participation within the trial (date, reason and category of status change) should be clearly documented in the source data.

11. ADVERSE EVENT REPORTING

11.1 Definitions

Standard definitions of different types of adverse events (AEs) are listed in Table 3.

Table 3: Adverse event reporting definitions

Severity Definitions	Mild	Awareness of signs or symptoms that do not interfere with the participant's usual activity or are transient and resolved without treatment and with no sequelae.
	Moderate	A sign or symptom, which interferes with the participant's usual activity.
	Severe	Incapacity with inability to do work or perform usual activities.
Adverse Event	AE	
Any untoward medical occurrence in a participant administered a medicinal product and which does not necessarily have a causal relationship with this intervention.
 
Comment:
 
An AE can therefore be any unfavourable and unintended sign (including abnormal laboratory findings), symptom or disease temporally associated with the use of an investigational medicinal product, whether or not related to the investigational medicinal product.

Adverse Reaction	AR	All untoward and unintended responses to an IMP related to any dose administered. Comment: An AE judged by either the reporting Investigator or Sponsor as having causal relationship to the IMP qualifies as an AR. The expression reasonable causal relationship means to convey in general that there is evidence or argument to suggest a causal relationship.
Serious Adverse Event	SAE	Any untoward medical occurrence or effect that: Results in death Is life-threatening* Requires hospitalisation or prolongation of existing hospitalisation Results in persistent or significant disability or incapacity Is a congenital anomaly/birth defect Or is otherwise considered medically significant by the Investigator**
Serious Adverse Reaction	SAR	An AR which also meets the definition of a SAE.
Unexpected Adverse Reaction	UAR	An AR, the nature or severity of which is not consistent with the applicable product information (e.g., Investigator Brochure for an unapproved IMP or (compendium of) Summary of Product Characteristics (SmPC) for a licensed product). When the outcome of an AR is not consistent with the applicable product information the AR should be considered unexpected.
Suspected Unexpected Serious Adverse Reaction	SUSAR	A SAR that is unexpected i.e., the nature, or severity of the event is not consistent with the applicable product information. A SUSAR should meet the definition of an AR, UAR and SAR.
Unexpected Event	UE	The type of event that is not listed in the protocol as an expected occurrence.
Related and Unexpected Serious Adverse Event	N/A	A SAE that meets both the definition of a Related and Unexpected Event.

* The term life-threatening is defined as diseases or conditions where the likelihood of death is high unless the course of the disease is interrupted.

** Medical events that may not be immediately life-threatening or result in death or hospitalisation but may jeopardise the participant or may require intervention to prevent one of the other outcomes listed in the definitions above.

11.2. Adverse event (AE) recording – general

The recording and reporting of AEs will be in accordance with the UK Policy Framework for Health and Social Care Research, the Principles of Good Clinical Practice (GCP) as set out in the UK Statutory Instrument (2004/1031; and subsequent amendments) and the requirements of the Health Research Authority (HRA) and The Medicines for Human Use (Clinical Trials) Regulations 2004 and amendments thereof. Definitions for adverse event reporting are listed in Table 3 in Section 11.

It is routine practice to record AEs in the participant's medical notes and it is also recommended that this includes the documentation of the assessment of severity and seriousness and also of causality (relatedness) in relation to the intervention(s) in accordance with the protocol.

11.3. Adverse event reporting in OXYPuF

As the use of ambulatory oxygen is part of the current standard of care for this participant population the collection of AE data is not in itself an outcome measure within the trial. Therefore AE data will not be collected although SAE data will be collected as per section 10.4.

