15.2.2 Secondary outcomes

Patient characteristics will be summarised using mean and standard deviation (SD) for continuous data.

Continuous secondary outcomes (e.g., K-BILD subscales, VAS for cough) will be analysed as per the primary outcome.

Categorical outcomes (e.g, Hospitalisations, Adverse events, Mortality) will be presented as frequency counts and percentages. Frequency of hospitalisations and adverse events will be analysed using Poisson regression techniques. Binary outcomes (Scheduled/Unscheduled health services use, Completion of pulmonary rehabilitation, Progress to LTOT) will be analysed using log-binomial regression model to calculate the adjusted relative risk and 95% confidence interval. Mortality data, will be analysed using Cox proportional hazard techniques given the assumptions of proportionality are met, and an adjusted hazards ratio with a 95% confidence interval will be presented.

Regarding safety, the total number of patients experiencing SAEs will be given by intervention group along with a descriptive table of the events, and statistical significance will be determined by a chi-square test.

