15.3 Planned final analyses

The primary analysis for the trial will occur once all participants have completed the 6 month assessment and corresponding outcome data has been entered onto the trial database and validated as being ready for analysis. This analysis will include data items up to and including the 6 month assessment and no further.

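### Section 11.3 says adverse event data will not be collected, which contradicts the targeted adverse event outcome, its row in Table 2 and its planned Poisson model

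*Protocol*

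**What the plan says.** On adverse events (AEs), the protocol takes two positions.

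- **Collected and analysed.** The trial summary and section 8.2.2.1 list "Targeted adverse events" among the secondary outcomes. Table 2 in section 9.1 has a row "Adverse events" marked at baseline, 3 months and 6 months. Section 15.2.2 states: "Frequency of hospitalisations and adverse events will be analysed using Poisson regression techniques".
- **Not an outcome, not collected.** Section 11.3 argues that ambulatory oxygen is already standard care, and concludes that "the collection of AE data is not in itself an outcome measure within the trial. Therefore AE data will not be collected". It makes a single exception, for serious events, and gives a cross-reference for it: "although SAE data will be collected as per section 10.4". Section 10 deals with withdrawal and has no 10.4; SAE reporting is in 11.4.

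On mortality, section 8.2.2.1 lists "Mortality (6 months, and from medical record only at 12 months". Section 15.2.2 says "Mortality data, will be analysed using Cox proportional hazard techniques", without a time horizon. Section 15.3 says of the primary analysis: "This analysis will include data items up to and including the 6 month assessment and no further".

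**The concern.** An unseen statistical analysis plan cannot repair this, because it cannot analyse data that sites have been told not to send.

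Two consequences are possible. If every site follows 11.3, the trial office holds no non-serious AE data, so a declared outcome and its regression cannot be produced. If some sites follow Table 2, AE counts will depend partly on which section the site followed. The trial is open label, so uneven capture could also differ between arms, and a Poisson comparison would then partly reflect reporting habits.

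At stake is the non-serious side of the benefit-harm comparison for an intervention judged on quality of life. The pilot is affected too: section 8.1.3 counts safety data as critical data, with receipt of at least 90% as green and 79% or less as red. What belongs to safety data therefore has to be settled before that rule is applied.

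**Working it through.** No figure in the plan bears on this point, so the check is a comparison of sections.

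**Adverse events**

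| Place | Are AEs an outcome, or collected? |
|---|---|
| Trial summary; 8.2.2.1 | Yes: targeted AEs are a secondary outcome |
| 9.1, Table 2 | Yes: AE row at baseline, 3 and 6 months |
| 15.2.2 | Yes: counts and percentages, and a Poisson model |
| 11.3 | No on both counts; SAEs only |
| 9, visit lists | Only SAE items, at 3 and 6 months; none at baseline |
| 12.2, Table 8 | Only an SAE form is named; the list is stated not to be exhaustive |

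1. *Could AEs in 15.2.2 be shorthand for SAEs?* Probably not. The same section has a separate sentence on SAEs, with a chi-square test on the number of patients affected. The Poisson sentence concerns the frequency of another quantity.
2. *Could the Table 2 row be the SAE check?* Possibly, since the section 9 lists name only SAEs at 3 and 6 months. But the row is also marked at baseline, where section 9 has no SAE item. Even on this reading, the outcome in 8.2.2.1 and the model in 15.2.2 remain in conflict with 11.3.
3. *Could targeted AEs be a subset that 11.3 does not cover?* Section 11.3 makes no exception except for SAEs, and no section lists the targeted events.
4. *What remains if 11.3 is followed?* SAEs remain, except that pre-planned hospitalisations and admissions under 24 hours are not reported on the SAE form (11.4.1). Hospitalisations also remain, as a separate secondary outcome. Non-serious events do not reach the trial office.

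**Twelve-month mortality**

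1. The 12-month time point is declared, from the medical record only.
2. Table 2 ends at 6 months, Table 8 names no 12-month form, and section 23 puts completion at 6 months after an individual's recruitment.
3. The 6-month cut in 15.3 is attached to the primary analysis. That is the only analysis described there, but nothing says that no other will follow.
4. Section 14 ties the end of trial to the last data capture, which leaves room for a record check.

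The time point is therefore not excluded, but it has no stated collection point or analysis.

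**Epworth scale.** It is a secondary outcome in the trial summary and 8.2.2.1 but has no row in Table 2, whereas K-BILD, IPAQ, cough and EQ-5D-5L do.

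**The case against.** The strongest reply is that little is lost. Section 11.2 notes that AEs are routinely written in the medical notes, and 11.5.1 prescribes causality categories for AEs in the source data. SAEs are collected and compared, hospitalisations are analysed, the risk category is no higher than standard care, and the primary outcome is untouched.

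Most of this stands. It would be wrong to infer from 11.3 that sites record no AEs or that the trial has no harm data. But routine notes are not a defined, uniformly elicited dataset, and 11.3 stops their transfer to the trial. The outcome and its model still lack data.

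A reader might also infer that 12-month mortality cannot be reported and that about half the deaths are thrown away. With the background section's median survival of about 3 years and a constant hazard:

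- by 6 months, 1 − 0.5^(0.5/3) = 10.9%, or 28.4 of 260;
- by 12 months, 1 − 0.5^(1/3) = 20.6%, or 53.6 of 260;
- share falling after 6 months, (53.6 − 28.4)/53.6 = 47%.

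The arithmetic is right but the inference is not supported. Those deaths are lost only if no later analysis takes place, and the protocol does not say that. A record check needs no visit, the Cox model has no 6-month limit, and the timing of a later analysis may well be in the analysis plan. The counts are also only illustrative: the median runs from diagnosis, while participants enter at any disease severity.

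Similarly, Epworth's absence from the section 9 lists shows nothing, because K-BILD and IPAQ are not named there either; questionnaires fall under the participant booklet.

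**Conclusion.** The AE contradiction is established by the protocol's own text and needs correcting. Its size is one declared secondary outcome and one planned model without a dataset if 11.3 is followed, or site-dependent capture if it is followed only in part. Serious events, hospitalisations and the primary outcome are unaffected. The conclusion assumes only that sites act on the protocol as written; a site instruction or form not shown here could already have settled the matter, but the protocol text would still need correcting. Non-serious events that are not elicited during follow-up cannot be recovered reliably afterwards, so timing matters.

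Twelve-month mortality and the Epworth scale are minor gaps in the schedule. Neither supports a claim that an outcome is lost.

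**What to change.** Reconcile the sections in one of two ways.

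- **Keep the outcome.** Replace the sentence in 11.3 with: *Only a pre-defined list of targeted AEs, named in this protocol, will be collected, at the time points in Table 2 and identically in both arms.* Add the list, whose content is for the clinical investigators to decide, and align the section 9 visit lists.
- **Drop the outcome.** Delete targeted AEs from the trial summary and 8.2.2.1, relabel the Table 2 row as SAEs, take AEs out of the categorical outcomes in 15.2.2, and limit the Poisson model to hospitalisations.

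In either case, correct the cross-reference in 11.3 from 10.4 to 11.4, and say in 8.1.3 what counts as safety data.

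Minor clarifications:

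- State when the 12-month record check and the 12-month mortality analysis take place, noting that section 7.6 allows ambulatory oxygen in either arm after the trial ends; or limit mortality to 6 months.
- Add an Epworth row to Table 2.

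The cost is amendment wording. Keeping the outcome adds a short checklist at existing visits, and keeping 12-month mortality adds one record look-up per participant. Dropping the AE outcome costs nothing at sites, but gives up any comparison of non-serious harms.

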11.4. Serious Adverse Advents (SAE) reporting in OXYPuF

For all SAEs, the PI or delegate must do one of the following:

- **Record safety reporting-exempt SAEs** in the medical notes but **not report** them to the trials office on an SAE form as per Section 0 11.4.1. Serious Adverse Events not requiring reporting to the Trial Office.
- **Report SAEs to the trial office in a non-expedited manner.** This can only be done for the pre-defined subset of SAEs as per Section 0 11.4.2 Serious Adverse Events requiring non-expedited reporting to the Trial Office.
- **Report SAEs to the trial office in an expedited manner** (within 24 hours of the site research team becoming aware of the event). All SAEs not covered by the above 2 categories must be reported as per Section 0 11.5. SAE Reporting process.

Note: when an SAE occurs at the same hospital at which the participant is receiving trial intervention or is being followed up for trial purposes, processes must be in place to make the trial team at the hospital aware of any SAEs, regardless of which department first becomes aware of the event, in an expedited manner.

11.4.1. Serious Adverse Events not requiring reporting to the Trial Office

At whatever time they occur during an individual's participation, from when intervention started to end of participant follow-up, the following are not considered to be critical to evaluations of the safety of the trial:

1. Pre-planned hospitalisation even if >24 hours
2. Hospital admissions lasting less than 24 hours

All events which meet the definition of serious must be recorded in the participant notes, including the causality and severity, throughout the participant's time on trial, including follow-up, but for trial purposes these events do not require reporting on the SAE Form. Such events are "safety reporting exempt".

11.4.2. Serious Adverse Events requiring non-expedited reporting to the Trial Office (expected SAEs)

OXYPuF participants are likely to have significant co-morbidities and therefore the frequency of SAEs may be high. Most of the SAEs occurring in OXYPuF will be anticipated in the sense that they are recognised and accepted complications/consequences of IPF.

The events outlined in Table 4 are regarding as expected SAEs, i.e. are recognised complications/consequences of IPF. These events should be reported in the participant's medical

records and on the OXYPuF SAE Form, and will not be subject to expedited reporting i.e. within 24 hours of the event, but should be reported within 2 weeks of the site research team becoming aware of these events. As such events will, by protocol definition be unrelated, rapid assessment of causality is not required.

Table 4 Expected SAEs that do not require expedited reporting

Acidotic hypercapnic respiratory failure
Right heart failure
Polycythaemia

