11.5.1. Assessment of causality of an SAE

When completing the SAE form, the PI (or, throughout this section, a medically qualified delegate) will be asked to define the nature of the seriousness and causality (relatedness; see table 5) of the event.

In defining the causality the PI must consider if any concomitant events or medications may have contributed to the event and, where this is so, these events or medications should be reported on the SAE form. It is not necessary to report concomitant events or medications which did not contribute to the event.

As per table 5, all events considered to be 'possibly', 'probably', or 'definitely' related to the intervention will be reported by the trial office as 'related'; all events considered at site to be 'unlikely' or 'unrelated' to the intervention will be reported by the trials office as 'unrelated'. The same categorisation should be used when describing AEs and protocol-exempt SAEs in the source data.

Table 5: Categories of causality

Category	Definition	Causality
Definitely	There is clear evidence to suggest a causal relationship, and other possible contributing factors can be ruled out.	Related
Probably	There is evidence to suggest a causal relationship, and the influence of other factors is unlikely.	
Possibly	There is some evidence to suggest a causal relationship. However, the influence of other factors may have contributed to the event (e.g., the participant's clinical condition, other concomitant events or medication)	
Unlikely	There is little evidence to suggest there is a causal relationship. There is another reasonable explanation for the event (e.g., the participant's clinical condition, other concomitant events or medication).	Unrelated
Not related	There is no evidence of any causal relationship.	

On receipt of an SAE Form, the Trial Office will forward it, with the unique reference number, to the Chief Investigator (CI) who will independently* review the causality of the SAE. An SAE judged by the PI or CI to have a reasonable causal relationship ("Related" as per Table 5) with the intervention will be regarded as a related SAE (i.e., SAR). The severity and causality assessment given by the PI will not be downgraded by the CI. If the CI disagrees with the PI's causality assessment, the opinion of both parties will be documented, and where the event requires further reporting, the opinion will be provided with the report.

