11.5.2. Assessment of expectedness of an SAE by the CI

The CI will also assess all related SAEs for expectedness with reference to the criteria in table 6.

Table 6: Categories of expectedness

Category	Definition
Expected	An adverse event that is consistent with known information about the trial related procedures or that is clearly defined in the relevant safety information found in the Baywater Medical Oxygen SmPC.
Unexpected	An adverse event that is not consistent with known information about the trial related procedures.

If the event is unexpected (i.e., it is not defined in the approved version of the Reference Safety Information (RSI)) it will be classified as a Suspected Unexpected Serious Adverse Reaction (SUSAR).

The CI will undertake review of all SAEs and may request further information from the clinical team at site for any given event(s) to assist in this.

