11.6. Reporting SAEs to third parties

The independent Data Monitoring Committee (DMC) may review any SAEs at their meetings.

The Trial Office will report details of all SARs (including SUSARs) to the MHRA, Research Ethics Committee (REC), and University of Birmingham (UoB) Research Governance Team (RGT) annually from the date of the Clinical Trial Authorisation, in the form of a Development Safety Update Report (DSUR).

Additionally, the Trial Office will report a minimal data set of all individual events categorised as a fatal or life threatening SUSAR to the MHRA, REC, and UoB RGT within 7 days of being notified. Follow-up information will be provided within an additional 8 days.

All other events categorised as SUSARs will be reported within 15 days of being notified.

Details of all SUSARs and any other safety issue which arises during the course of the trial will be reported to the PIs. A copy of any such correspondence should be filed in the ISF and Trial Master File (TMF).

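### The exemption for hospital admissions under 24 hours makes no exception for related events, so a related short admission misses the SAE Form and with it central causality and SUSAR review

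*Protocol*

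**What the plan says.** Protocol section 11.4 sorts every SAE into one of three routes: exempt, non-expedited, or expedited. Exempt SAEs are recorded "in the medical notes but not report them to the trials office on an SAE form". Expedited reporting takes what is left: "All SAEs not covered by the above 2 categories must be reported".

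Section 11.4.1 names two exempt categories, pre-planned hospitalisation and "Hospital admissions lasting less than 24 hours". The reason given is that "the following are not considered to be critical to evaluations of the safety of the trial". Causality and severity still go in the participant's notes, but "for trial purposes these events do not require reporting on the SAE Form". Section 11.5.1, after setting out the five-level causality scale, adds: "The same categorisation should be used when describing AEs and protocol-exempt SAEs in the source data".

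Section 11.5.2 states that "The CI will undertake review of all SAEs", and that every related SAE is assessed for expectedness. Section 11.6 states that "The Trial Office will report details of all SARs (including SUSARs) to the MHRA" and others each year, with individual SUSARs reported within 7 or 15 days of notification.

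**The concern.** The rule filters by length of stay and not by relevance to safety. Sites are told to grade exempt SAEs on a scale that runs up to definitely related, so the protocol foresees an exempt event that the PI attributes to oxygen. It then gives that judgement no path out of the site.

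Oxygen is the investigational product here (section 7.1), and the trial runs under a Clinical Trial Authorisation (section 19). At stake is whether a related, unexpected serious event with a short stay can be recognised as a SUSAR at all. Also at stake is whether the SAE comparison by arm in section 15.2.2 counts every participant it claims to count.

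**Working it through.** No arithmetic applies. The check traces one case through the sections: an unplanned admission under 24 hours that the PI judges possibly related to oxygen.

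1. **Is it serious?** Yes. Table 3 lists hospitalisation as a seriousness criterion and sets no minimum stay.
2. **Is it a serious adverse reaction?** Yes. Under section 11.5.1 an SAE judged related by either the PI or the CI counts as one, and possibly related falls on the related side of Table 5.
3. **Does it go on an SAE Form?** No. Section 11.4.1 exempts it on duration alone. Section 11.4 keeps exempt events out of the expedited route. Section 11.4.3 names no exception, and its cross-reference prints as section 0, so it settles nothing.
4. **Does the CI review causality?** No. Section 11.5.1 starts that review when the Trial Office receives the form.
5. **Is expectedness assessed?** No. Section 11.5.2 places this with the CI, who has not been told of the event.
6. **Is it reported onward?** It cannot be. The 7- and 15-day periods in section 11.6 run from notification, which never happens.
7. **Is it in the SAE comparison?** Not if that comparison is built from SAE Forms, the only SAE record in Table 8. The visit lists in section 9 include SAE checks at 3 and 6 months, but an exempt event found there falls under the same rule.

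Steps 2 and 6 conflict: the event is a serious adverse reaction by the protocol's definition, section 11.6 promises to report all of these, and sections 11.4 and 11.4.1 tell the site not to send it.

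The contrast with section 11.4.2 is useful. The Table 4 events are declared unrelated by protocol definition, which explains their lighter handling. No such declaration is made for short admissions.

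A second case is a death within 24 hours of admission. Read literally, item 2 covers it. Read as addressing only the hospitalisation criterion, it does not, because Table 3 lists death separately. The text does not choose. Even on the literal reading, the death reaches the Trial Office through the change of status CRF (Table 8), the survival checks (section 9) and the mortality outcome (section 8.2.2.1). Only the SAE Form and the review it triggers are lost.

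**The case against.** **Risk-adapted reporting is deliberate.** The trial is rated Type A (section 3.4), with oxygen used within its marketing authorisation (section 7.7.2). Sparing sites a form for each unrelated short stay is reasonable. This stands, and the fix preserves it. The rating does not remove the commitments in section 11.6.

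**The conflict may be one of scope.** Section 11.5.2 describes what follows receipt of a form, so the CI's review of all SAEs could mean all those submitted. That reading is fair for that sentence. It does not rescue section 11.6, because PI judgement alone makes an SAE a serious adverse reaction.

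**Stronger readings that a reader might infer are not supported:**

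- *Fatal events stop in the site notes and never reach the Data Monitoring Committee (DMC).* Deaths arrive by the separate routes above, and section 18.5 supplies safety outcome data to the DMC. A site may also reasonably treat a death as a death and not as a short admission.
- *Short admissions disappear from the data.* All-cause hospitalisation is a secondary outcome with no length-of-stay limit and is analysed by arm (sections 8.2.2.1 and 15.2.2). What those counts lack is central causality assessment.
- *Causality is never assessed.* The site must record it. The independent CI review is what is missing.
- *SAE Forms are the only safety data.* Section 11.3 says AE data are not collected, but section 8.2.2.1 lists targeted adverse events, Table 2 schedules adverse events and section 15.2.2 analyses them. Section 11.3 cannot be relied on alone.
- *A definite number of events is withheld.* The documents give no admission rate, no share of short stays and no share judged related, so any such count would rest on unsourced inputs.

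**Conclusion.** The point holds in a limited form. As written, a short admission that the PI judges related has no stated route to CI causality review, expectedness assessment or SUSAR reporting, and it drops out of an SAE comparison built on the forms. This conflicts with sections 11.5.2 and 11.6. For events serious on another ground, the text is ambiguous and sites may apply it differently.

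The loss is the form and the central review, not knowledge of the event. Its size cannot be estimated from the documents. Only the oxygen arm, about 130 of 260 participants at 1:1 allocation, can have events related to oxygen, and the number may be small. The conclusion does not depend on frequency, since a single related short admission would leave section 11.6 unmet. It assumes that sites follow section 11.4.1 literally and that no form other than the SAE Form carries PI causality to the Trial Office; none is described. The protocol should be corrected, but this is not a fault that undermines the trial: should-fix.

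**What to change.** Reword item 2 of section 11.4.1 so that an admission under 24 hours is exempt from the SAE Form only if both conditions hold:

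- hospitalisation is its sole seriousness criterion, so that it is not also fatal, life-threatening, disabling or otherwise medically significant under Table 3; and
- the PI judges it unrelated to the trial intervention, using the Table 5 grouping.

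All other short admissions are reported under section 11.5. Bring sections 11.4, 11.4.3 (including its broken cross-reference), 11.5.1, 11.5.2 and 11.6 into line, so that the stated scope of CI review and of reaction reporting matches what sites are told to send.

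The cost is a wording amendment, a reminder to sites and a few extra SAE forms. Sites already record causality for exempt events, so the second condition needs no new assessment.
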